## **3 STUDY DESIGN**

### **3.1 Overall Design**

This is a multicenter, open label, non-randomized, Phase 2 study of HBI-8000 in combination with a Food and Drug Administration (FDA) approved dose of pembrolizumab as the first checkpoint inhibitor therapy for advanced or metastatic NSCLC where subjects have programmed death ligand 1 (PD-L1) expression Tumor Proportion Score (TPS)  $\geq 1\%$ . Prior to enrollment, the PD-L1 expression status must be available. Historical data may be used to assess for eligibility. If historical data is not available, tumor tissue will be analyzed locally by an FDA-approved test to yield PD-L1 status prior to enrollment.

The dose of HBI-8000 is 30 mg twice weekly. Pembrolizumab is administered according to prescribing information.

The study will include a screening period of up to 28 days before the first dose of HBI-8000. Study Treatment may be with or without pembrolizumab. HBI-8000 and pembrolizumab will continue up to 24 months. HBI-8000 will continue until disease progression, unacceptable toxicity related to HBI-8000 ensues or withdrawal of informed consent to receive HBI-8000.

The Treatment Phase allows for up to 24 months of treatment (cycles are 21 days), providing the subject does not experience disease progression or unacceptable toxicity. An End of Treatment safety visit will be performed 30 ( $\pm 3$ ) days after last dosing of HBI-8000. If HBI-8000 is discontinued due to unacceptable toxicities related to HBI-8000, pembrolizumab may continue as single agent under standard of care. Subjects will be followed for up to 12 months after the last dose of HBI-8000 for disease status, including initiating a new cancer treatment and experiencing disease progression, death, or becoming lost to follow-up or consent withdrawal.

### **3.1.1      Expected Duration of Subject Participation**

Subject participation duration from screening through end of treatment visit is approximately up to 38 months, including:

Screening period:	Up to 28 days
Treatment period:	Until radiographic disease progression per RECIST v1.1 (assessed by the Investigator), unacceptable toxicity, or other reasons for discontinuation with a maximum treatment duration of 24 months, unless there is an agreement between the Sponsor and the Investigator to allow HBI-8000 beyond 24 months.
Short-term Follow up/ End of treatment (EoT) period	Up to 30 days ( $\pm 3$ days) after the last dose HBI-8000. This will be defined as EoT.
Long-term Follow-up period:	Every 12 weeks (3 months) up to a maximum of 12 months after the last dose of HBI-8000.

### **3.1.2      Tumor Status and Survival Follow-Up**

Subjects without disease progression who completed up to 24 months of treatment or discontinued from HBI-8000 due to reasons other than PD are followed with imaging studies every 12 ( $\pm 1$ ) weeks until progression is documented, another anti-cancer treatment is initiated, or referral to hospice, whichever occurs first.

All subjects will be contacted approximately every 12 ( $\pm 1$ ) weeks by telephone contact or e-mail for survival follow-up for up to 12 months after the last dose of HBI-8000.

### **3.1.3      Study Population**

Approximately 20-24 subjects with advanced or metastatic non-small cell lung cancer will be enrolled at approximately 6-10 investigational sites in the United States. Subjects that have signed an informed consent but did not receive HBI-8000 may be considered for this study provided they are re-consented and undergo screening procedures specified in the protocol.

Under no circumstances will subjects who enroll in this study and have completed treatment as specified, be permitted to enroll for a second time.

## **3.2      Justification for Dose**

The Sponsor plans to evaluate HBI-8000 at 30 mg orally twice a week (BIW) in combination with pembrolizumab administered intravenously at 400 mg every 6 weeks or 200 mg every 3 weeks in the present study (HBI-8000-305). This dosing regimen was selected based on clinical observations related to safety, tolerability, PK, and efficacy from previously conducted Phase 1b/2 study (HBI-8000-302).

## **3.3      End of Treatment Definition**

The end of treatment is defined as the date of the last dose of HBI-8000 taken by the subject.

### **3.4 End of Study Definition**

The study completes when all subjects have experienced progressive disease or 12 months after the last dose of HBI-8000 administration, whichever comes first. All subjects will be followed until death, lost to follow-up, withdrawn consent from study participation entirely, or study terminated by Sponsor.

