- b. End-of-Treatment Safety Follow-Up visit, performed 30 ± 3 days after the last day of HBI-8000 administration, or before the initiation of new cancer treatment, whichever is earlier.
- c. Informed consent must be obtained prior to initiation of any study-specific procedures.
- d. Cancer diagnosis must include known mutation status for BRAF V600, EGFR, and ALK.
- e. Temperature, heart rate, diastolic and systolic blood pressure after subject is in a supine position for at least 5 minutes.
- f. Complete physical exam at baseline. Symptom directed physical exam for screening and all other cycles.
- g. Standard 12-lead ECG will be done using local standard procedures at Baseline and at End of Treatment Safety Follow-Up visits.
- h. MRI performed per institutional guidelines and practice, and if clinically indicated for subjects with documented brain metastasis.
- i. Historical data may be used to assess for eligibility. If historical data is not available, tumor tissue will be analyzed locally by an FDA-approved test to yield PD-L1 status prior to enrollment.
- j. Hematology panel to include hemoglobin, hematocrit, red blood cell count, white blood cell count, differential, platelet count.
- k. Chemistry panel to include BUN, creatinine, AST, ALT, LDH, total bilirubin (including direct fraction if total bilirubin abnormal), lipase, amylase, TSH, T4 free (direct), total protein, albumin, uric acid, alkaline phosphatase, sodium, potassium, calcium, magnesium, phosphorus, and glucose.
- l. Urinalysis: dipstick followed by microscopic examination, if abnormal results.
- m. For women of childbearing potential (including those with tubal ligation): Serum pregnancy test at baseline (within 14 days of starting treatment) and at the end of treatment.
- n. Hepatitis B and Hepatitis C testing to include HBsAg, anti-HCV antibodies.
- o. HBI-8000 should be administered twice a week approximately 30 minutes after a meal.
- p. Pembrolizumab 400 mg every 6 weeks or 200 mg every 3 weeks on Day 1 of each Cycle should be administered as intravenous (IV) infusion over 30 minutes and in accordance with the manufacturer package insert and institutional practice.
- q. Tumor assessment of all lesions by radiographic or other modality (CT, MRI). Tumor assessments to be performed at Screening, and Day 1 of Cycles 3, 5, 7, etc. every 6 weeks (± 3 days) thereafter until PD.

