## **4.4 Withdrawal Criteria**

### **4.4.1 Subject Withdrawal from the Study**

Subjects may withdraw from the study at any time for any reason. The Investigator should try to ascertain the reason for withdrawal as completely as possible. The Investigator may also decide to discontinue a subject from the study. HBI-8000 may be discontinued, and the subject withdrawn from the study under the following circumstances:

- Unacceptable toxicity (AE)
- Progression of the disease under study
- Decision by the Investigator or subject to permanently discontinue HBI-8000
- Intercurrent illness that would, in the judgment of the Investigator, affect clinical assessments, patient safety, or follow-up to a significant degree
- Significant protocol deviations that jeopardize the usefulness of the data

- Subject noncompliance, examples include omitting >1/3 of protocol specified dose over 6 consecutive weeks, not adhering scheduled safety assessments, etc.
- Subject is beginning another anti-cancer treatment
- Subject becomes pregnant
- Subject request to withdraw informed consent
- Death

All subjects who withdraw from HBI-8000 must complete an EoT safety follow-up visit, to be performed 30 ( $\pm$  3) days after the last dose of HBI-8000, or before initiation of new cancer treatment, whichever is earlier. After HBI-8000 is discontinued, the subjects should be followed for disease progression (if not already recorded) and survival. Only subjects who have withdrawn from study participation entirely, including the period after HBI-8000 is discontinued, will not be followed. In other words, a subject may withdraw consent for treatment but still allow follow-up, in which case he/she should be followed for safety, survival, and disease status.

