#### **6.2.2.4.6 Follow-Up of Adverse Events**

Subjects should be asked to specifically describe any signs, symptoms, or AEs (regardless of relationship to Study Treatment) they may notice prior to the start of the study or thereafter. At a minimum, subjects should be asked to report any changes at each visit to the study center. Conditions that the subject experienced prior to informed consent should be recorded in the medical history section of the eCRF.

AEs, Grade 2 and above, considered to be at least possibly related to the Study Treatment must be followed up after the EoT assessment until the events have resolved, returned to the baseline level, are judged by the Investigator to be stable, or no longer require follow up provided the subject is withdrawn from the study due to initiation of new therapy or consent withdrawal for further follow-up. AEs that are assessed by the Investigator as unrelated to Study Treatment will be followed only to the EoT visit. The outcome of any AEs which do not resolve will be recorded as "ongoing" on the eCRF.

Serious adverse events (SAE) and adverse events of special interest (AESI), namely immune-related toxicities, will be collected for up to 90 days following cessation of treatment or 30 days following cessation of treatment if the subject initiates new anticancer therapy, whichever is earlier.

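### The end-of-study rule lets the trial complete at the last progression, before follow-up that other sections require; survival contact is the main loss, and safety collection is put in conflict

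*Combined protocol and SAP*

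**What the plan says.** Section 3.4 (End of Study Definition) has two sentences. The first sets completion: "The study completes when all subjects have experienced progressive disease or 12 months after the last dose of HBI-8000 administration, whichever comes first". The second reads: "All subjects will be followed until death, lost to follow-up, withdrawn consent from study participation entirely, or study terminated by Sponsor".

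Other sections set duties that run from the last dose:

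- **Safety visit.** Section 4.4.1: "All subjects who withdraw from HBI-8000 must complete an EoT safety follow-up visit". Progression is one of the listed reasons for stopping. The Table 1 footnote times the visit: "performed 30 ± 3 days after the last day of HBI-8000 administration, or before the initiation of new cancer treatment, whichever is earlier". Section 6.1.4 repeats this.
- **Serious and special-interest events.** Section 6.2.2.4.6: these "will be collected for up to 90 days following cessation of treatment", or for 30 days if new anticancer therapy starts.
- **Adverse events that led to permanent discontinuation.** Section 6.3 follows these past progression until they resolve, are stable, or the subject is lost.
- **Survival.** Section 3.1.2 has all subjects contacted "by telephone contact or e-mail for survival follow-up for up to 12 months after the last dose of HBI-8000". Section 6.2.1.1.2 gives the same limit.

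Two sections make survival contact depend on the end-of-study date: 6.1.5 stops it at death or study end, and 6.2.1.1.2 runs it to study completion.

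On timing of progression, section 3.1 says "HBI-8000 will continue until disease progression, unacceptable toxicity related to HBI-8000 ensues". The Synopsis and section 3.1.1 give a duration of about 38 months.

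**The concern.** HBI-8000 is given until progression, so by default progression falls at or close to the last dose. Under the earlier-of-two-events rule, progression of the last remaining subject completes the study at a point when that subject has only just stopped treatment. The follow-up timed from the last dose then lies after completion. Earlier progressors who are still within 12 months of their last dose lose survival contact as well.

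Safety and tolerability of the combination is a secondary objective (section 2.2). The special-interest events are the immune-related toxicities, which can appear late, and with 20 to 24 subjects each late event carries weight. End of study is also an operational trigger: sites cannot follow section 3.4 and the follow-up sections together when the progression condition is met first.

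**Working it through.** **1. Reproduce the stated duration.** Inputs from the Synopsis: screening 28 days (28/30.44 = 0.92 month), treatment 24 months, safety follow-up 1 month, survival follow-up 12 months.

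- Components added: 0.92 + 24 + 1 + 12 = 37.9 months, which matches the stated 38.
- With the 12 months counted from the last dose, as worded: 0.92 + 24 + 12 = 36.9 months.
- If the last subject progresses at treatment month 24 and the study completes that day: 0.92 + 24 = 24.9 months for that subject, which is 12 to 13 months short.

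The stated duration therefore fits only if follow-up after the last dose is carried out.

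**2. What is cut, by timing of the last progression.** Put the last subject's last dose at day 0 and progression, hence completion, at day L. Days lost are max(0, 90 − L) for serious and special-interest events and max(0, 365 − L) for survival. The 12-weekly contacts are taken at days 84, 168, 252 and 336.

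| L (days) | 30-day visit | Event-window days lost | Survival days lost | Contacts lost |
|---|---|---|---|---|
| 0 | after completion | 90 | 365 | 4 |
| 30 | on completion date | 60 | 335 | 4 |
| 90 | done | 0 | 275 | 3 |
| 180 | done | 0 | 185 | 2 |
| 365 | done | 0 | 0 | 0 |

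**3. How often the progression condition comes first.** This needs assumptions the documents do not supply:

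- n = 24; accrual uniform over 12 to 18 months (assumed).
- Exponential time to progression with medians of 4.9 and 8.8 months, the PFS medians of the two arms of the first-line pembrolizumab-plus-chemotherapy trial described in section 1.1.1, plus an assumed middle value of 6.5.
- Dosing until progression or 24 months. T1 = date of the last progression. T2 = last dose taken by any subject + 12 months. The progression condition governs if T1 < T2.

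With every progression documented, 40,000 simulated trials per setting give P(T1 < T2) of 0.88-0.90 (median 4.9), 0.66-0.70 (6.5) and 0.32-0.36 (8.8).

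The condition also requires documented progression in every subject. With an assumed independent per-subject probability q, multiply by q^24:

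| q | q^24 | Low: 0.32 × q^24 | High: 0.90 × q^24 |
|---|---|---|---|
| 1.00 | 1 | 32% | 90% |
| 0.95 | 0.292 | 9% | 26% |
| 0.90 | 0.080 | 2.5% | 7% |
| 0.80 | 0.0047 | 0.2% | 0.4% |

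**4. What is open when it does come first (n = 24).** On average 3.4-5.8 subjects are less than 12 months past their last dose (deaths not removed), and 0.4-1.2 are inside 90 days. At least one subject is inside 30 days in about 15-63% of those trials. In the rest, the last progressor has already been off drug longer than that, for example after reaching the 24-month cap.

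**The case against.** The strongest answer is that the progression condition will seldom be met. One subject without documented progression leaves the 12-month condition in control. The protocol makes such subjects likely: imaging stops at new anticancer treatment or hospice referral (sections 3.1.2 and 6.1.5), and subjects may die, withdraw or be lost. This stands. A reader might infer from the simulation that the problem arises in 32-90% of trials, but that range holds only at q = 1, and the documents give no value for q.

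The inputs are also only illustrative. Both medians come from chemotherapy-based arms and count deaths as events, whereas a death without progression does not satisfy section 3.4. Section 1.1.1 reports that 34-37% of responders to another PD-1 inhibitor had ongoing responses after at least 2 years; a tail that long would lower the probability further. This stands too.

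A reader might also infer that the last subject's safety visit and event window are always cut off, or that late safety events are certain to be lost. The documents do not support that. The safety duties are timed per subject from the end of treatment and are not made conditional on the study being open; only survival contact is. The 90 days and 12 months are ceilings. The safety part is therefore a conflict between sections, not an established loss.

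The second sentence of section 3.4 might be offered as the cure. It is not: following subjects until death contradicts the first sentence and also overruns the 12-month limit on survival contact.

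**Conclusion.** Section 3.4 is wrong as written, as an internal inconsistency. That conclusion rests on the text alone and needs no probability: an earlier-of-two-events rule cannot be followed together with sections 3.1.2, 4.4.1, 6.1.4, 6.2.2.4.6 and 6.3 when the last subject progresses on or near treatment, nor with its own second sentence, nor with the 38-month duration.

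The firm loss is survival follow-up, because sections 6.1.5 and 6.2.1.1.2 end it at study end. Up to 365 days can be lost for the last subject, and less for earlier progressors. Safety collection is put in conflict only when the last progression falls within about 30 days (visit) or 90 days (event window) of a subject's last dose.

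Frequency cannot be settled from the documents. Under the assumptions shown it runs from under 0.5% to 90%, driven mainly by the chance that every subject has documented progression. The effect on the planned efficacy analyses is small: all subjects have progressed by then, so ORR, DCR, DoR and PFS are little affected, and overall survival is neither an objective nor an endpoint.

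**What to change.** Reconcile section 3.4 with sections 3.1.2, 4.4.1, 6.1.4, 6.1.5, 6.2.1.1.2, 6.2.2.4.6 and 6.3. Define study completion as the date on which the last subject has completed the follow-up already specified (the EoT safety visit, the window for serious and special-interest events, and follow-up up to 12 months after the last HBI-8000 dose), or has died, withdrawn entirely or been lost. Align the second sentence of 3.4 with the 12-month limit, so that one rule governs survival contact.

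The change is one of wording and adds no visit or assessment. Its cost is a possibly later close-out, which stays within the roughly 38 months per subject already stated.

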## **4 STUDY POPULATION**

### **4.1 Inclusion Criteria**

Subjects may be entered in the study only if they meet all of the following criteria:

1. Adults at least 18 years of age.
2. Eastern Cooperative Oncology Group (ECOG) performance status  $\leq 2$ .
3. Histopathologically confirmed diagnosis of NSCLC PD-L1 expression TPS  $\geq 1\%$  as determined by an FDA-approved test.
4. Have at least one measurable target lesion as defined by RECIST v.1.1.
5. Have not received immune checkpoint inhibitor therapy or more than one regimen of chemotherapy for advanced or metastatic disease. Subjects who have previously received immune checkpoint inhibitor therapy in the adjuvant or neoadjuvant setting may be allowed if disease progression occurred  $>6$  months after the last dose and no clinically significant immune related toxicities leading to treatment discontinuation were observed.
6. Prior adjuvant or neoadjuvant systemic therapy with chemotherapy, EGFR or ALK mutation directed therapy must have been completed  $>4$  weeks before Cycle 1 Day 1 (C1D1) dosing and recovered from all treatment related toxicity.
7. Any prior palliative radiotherapy or minor surgery must be completed at least 2 weeks and 1 week respectively before C1D1 dosing and recovered from all treatment related toxicities.
8. Adequate major organ functions at baseline as evidenced by laboratory findings within 14 days prior to C1D1 study drug administration as defined below:
  - a. White blood cells (WBC)  $\geq 3000/\mu\text{L}$ , neutrophils  $\geq 1500/\mu\text{L}$ , platelets  $\geq 100 \times 10^3/\mu\text{L}$ , hemoglobin  $\geq 9.0 \text{ g/dL}$ , independent of transfusion.
  - b. Serum creatinine  $\leq 1.5 \text{ mg/dL}$ , normal electrolytes, phosphorus, and calcium,
  - c. Aspartate aminotransferase (AST) and alanine aminotransferase (ALT)  $\leq 3 \times$  upper limit of normal (ULN), alkaline phosphatase  $\leq 2.5 \times$  ULN unless bone metastases present, bilirubin  $\leq 1.5 \times$  ULN (unless known Gilbert's disease where it must be  $\leq 3 \times$  ULN) and serum albumin  $\geq 3.0 \text{ g/dL}$ .
  - d. Thyroid stimulating hormone (TSH) within normal limits.
9. Life expectancy  $\geq 12$  weeks.
10. A negative serum pregnancy test at baseline for women of childbearing potential (WOCBP).

11. Females of childbearing potential (non-surgically sterile or premenopausal female capable of becoming pregnant) and all males (due to potential risk of drug exposure through the ejaculate) must agree to use an acceptable method of contraception while enrolled on this study and for 5 months after the last dose of study drug. Acceptable methods of birth control in this trial include 2 highly effective methods of birth control (as determined by the Investigator; one of the methods must be a barrier technique) or abstinence.
12. Have the ability to understand and the willingness to sign a written informed consent document.

## 4.2 Exclusion Criteria

Subjects who fulfill **any** of the following criteria at screening will **not** be eligible for admission into the study:

1. History of Grade  $\geq 3$  or above hypersensitivity reactions to monoclonal antibodies.
2. History of a cardiovascular illness including: QT interval corrected by heart rate using Fridericia's correction formula (QTcF)  $>450$  ms in male or  $>470$  ms in female, congenital long QT syndrome, congestive heart failure (New York Heart Association Grade III or IV) ([Appendix 2](#)); unstable angina or myocardial infarction within the previous 6 months; or symptomatic cardiac arrhythmia despite medical management.
3. Uncontrolled hypertension, systolic blood pressure (SBP)  $>160$  mmHg or diastolic blood pressure (DBP)  $>100$  mmHg.
4. Central nervous system metastasis or leptomeningeal disease except when treatment of brain metastasis is completed  $>14$  days prior to C1D1 and stable for  $\geq 4$  weeks on  $<10$  mg daily prednisone or equivalent.
5. History of hemorrhagic diarrhea, inflammatory bowel disease, active uncontrolled peptic ulcer disease or bowel resection that affects absorption of orally administered drugs.
6. Recurrent pleural effusion requiring repetitive palliative thoracentesis within 3 months prior to study entry, except for subjects with a pleurex port.
7. Active, known, or suspected autoimmune disease, or history of immune-mediated toxicity leading to treatment discontinuation, except for type I diabetes mellitus, hypothyroidism only requiring hormone replacement or skin disorders (such as vitiligo, psoriasis, or alopecia) not requiring systemic therapy.
8. Active pneumonitis, history of non-infectious pneumonitis that required treatment with steroids, or history of interstitial lung disease.
9. Active uncontrolled bacterial, viral, or fungal infection requiring systemic therapy.
10. Known history of testing positive for human immunodeficiency virus (HIV), known acquired immunodeficiency syndrome (AIDS).
11. Active hepatitis B (serum hepatitis B surface antigen [HBVsAg] positive), or hepatitis C (HCV antibody test or serum hepatitis C ribonucleic acid [RNA] positive).
12. Received approved live vaccines within 30 days of planned C1D1. Inactivated viral vaccines or vaccines based on subviral component are allowed; however intranasal influenza vaccines (e.g. Flu-Mist) are not allowed. COVID-19 vaccination should be administered  $>7$  days before C1D1.

13. Any condition requiring chronic systemic treatment with either corticosteroids (>10 mg daily prednisone equivalents) or other immunosuppressive medications, or steroids use within 14 days of study drug administration. Inhaled or topical steroids are permitted.
14. Use of other investigational agent (drug not marketed for any indication) within 28 days or at least 5 half-lives (whichever is shorter) before study drug administration.
15. Pregnant or breast-feeding women.
16. Second malignancy unless in remission for 2 years; subjects with non-melanomatous skin cancer, carcinoma in situ of the cervix treated with curative intent, or curatively treated prostate cancer with prostate-specific antigen (PSA) <2.0 ng/mL can be included.
17. Underlying medical conditions that, in the Investigator's opinion, will make the administration of study drug hazardous or obscure the interpretation of toxicity determination or adverse events.
18. Unwilling or unable to comply with procedures required in this protocol.

